## 15.8 Study Reporting Requirements

By participating in this study, the investigator agrees to submit SAE reports according to the timeline and method outlined in this protocol. In addition, the investigator agrees to submit annual reports to his/her IRB as appropriate.

Upon completion or termination of the study, the principal investigator (PI) must submit a final written report to the Sponsor and IRB. The report must be submitted within 3 months (90 days) of completion or termination of the trial.

The Sponsor will submit all reports required by the appropriate regulatory authorities, including unanticipated adverse device effects, withdrawal of IRB approval, list of current investigators, annual progress reports, recall information, final reports and protocol deviations.

## 15.9 Selection of Investigators

The Sponsor will select qualified investigators, ship devices only to participating investigators, obtain a signed Investigator's Agreement and provide all investigators with the information and training necessary to conduct the study.

### 15.9.1 Financial Disclosure

Investigators and sub-investigators are required to provide financial disclosure information to allow the Sponsor to submit the complete and accurate certification or disclosure statements required under 21 CFR 54. In addition, the investigator must notify the Sponsor promptly of any relevant changes that occur during the course of the study, at the completion of the study, and 1 year following the completion of the study.

### 15.9.2 Investigator Documentation

Prior to beginning the study, the investigator will be asked to comply with 21 CFR 812 by providing the following essential documents, including but not limited to:

- An investigator-signed Investigator Agreement page of the protocol
- An IRB approved informed consent, samples of clinical site advertisements for recruitment for this study, and any other written information regarding this study that is to be provided to the subject
- IRB approval of the investigator, protocol, and acknowledgement of the user guide
- Curricula vitae (CV) for the PI and each investigator participating in the study. Current licensure must be noted on the CV or a copy of the license provided. CVs must be signed and dated by the investigators within 1 year of study start-up, indicating that they are accurate and current.
- Financial disclosure information (as stated above) and a commitment to promptly update this information if any relevant changes occur

- Laboratory certifications and normal ranges for any local laboratories used by the clinical site.

### **15.10 Clinical Site Training**

The training of appropriate clinical site personnel will be the responsibility of the Sponsor or its designee. To ensure proper device usage, uniform data collection, and protocol compliance, the Sponsor or designee will present formal training sessions to relevant clinical study site personnel. Clinical study personnel trained by the Sponsor may also train additional clinical study personnel at their site. The Sponsor reserves the right to enforce retraining for clinical sites who have demonstrated study or procedure compliance issues. Protocol-specific training will occur for all research personnel and key ancillary staff who will be involved in subject care.

### **15.11 Device Use**

The Omnipod Horizon™ System consists of the following primary components: an Omnipod Horizon™ Pod, Omnipod Horizon™ Controller, and the iCGM.

The Pod and PDM are intended for single use only. The PDMs will be returned to the Sponsor after completion of the study.

The Dexcom G6 CGM sensor (the component of the system that enters the skin), the Dexcom G6 CGM transmitter (the component of the system that attaches to the sensor to transmit the signal), and the Dexcom G6 CGM receiver will all be single use only in this study. The Dexcom G6 receiver will be returned to the Sponsor after completion of the study.

Study blood glucose meters and ketone meters will not be cleaned or reused by subjects. A new meter will be used for each subject.

### **15.12 Device Returns**

Any unused or damaged investigational devices or investigational devices related to a suspected deficiency or adverse event must be returned to the study Sponsor. To initiate the return, the clinical site will contact the Sponsor representative and provide the following information:

- Part number/Lot number
- Quantities
- Tracking number

### **15.13 Policy for Publication and Presentation of Data**

All data and results and all intellectual property rights in the data and results derived from the study will be the property of the study Sponsor, Insulet.

#### **15.14 Sponsor or Regulatory Agency Termination of the Study**

Although the Sponsor intends to complete the study, the Sponsor reserves the right to stop the study at any time for clinical or administrative reasons, or if required by the local regulatory authority, with suitable written notice to the investigators and regulatory authorities as appropriate.

Similarly, investigators may withdraw from the study by providing written notification to the Sponsor within 30 days of intent to withdraw. However, the Sponsor and investigators will be bound by their obligation to complete the follow-up of subjects already enrolled in the trial. Subjects must be followed according to the clinical protocol and information obtained during subject follow-up shall be reported on the eCRF.

## APPENDIX A

OMNIPOD HORIZON™ AUTOMATED GLUCOSE CONTROL SYSTEM  
PUMP THERAPY ORDER FORM

Investigator Site Use Only. Confidential: Protected Health Information

Subject Name \_\_\_\_\_ Date \_\_\_\_\_ / \_\_\_\_\_ / \_\_\_\_\_

Subject DOB \_\_\_\_\_ Subject Weight \_\_\_\_\_ Subject ID# \_\_\_\_\_

Standard Therapy Regimen \_\_\_\_\_ = \_\_\_\_\_ units Total Daily Dose (Pre-Pump)

## Dosing Calculation Section (optional)

Total Daily Dose (TDD) for pump calculations			
Pre-Pump TDD _____ units	Weight-based _____ kg OR _____ lbs.		
Pre-Pump TDD x 0.75 = Pump TDD _____ units/day x 0.75 = _____ units	Weight kg x 0.5 or lbs x 0.23 _____ kg x 0.5 = _____ units OR _____ lbs. x 0.23 = _____ units		
If Pre-Pump TDD and Weight-based are compared consider the following:  Average value of Pre-Pump and weight based methods  Hypoglycemic patients – use more conservative lower value  Hyperglycemic patients, elevated A1C – use higher value			
Pump TDD = _____ units			
Basal Rate			
Total Daily Basal (Pump TDD x 50% = Total Daily Basal)	_____ units/day x 0.5 = _____ units		
Initial Basal Rate (Total Daily Basal / 24 hours = Initial Basal Rate)	_____ units/24 hours = _____ U/hr		
Bolus Settings			
Insulin to Carb Ratio (450/TDD = Insulin to Carb Ratio)	450/_____ TDD units/day = _____ grams/unit		
Correction Factor (1700/Pump TDD = Correction Factor)	1700/_____ Pump TDD units/day = _____ mg/dL/unit		
Initial Pump Settings (required)  Transfer Pump Settings			
Basal			
Max Basal Rate _____ U/hr			
Basal 1	Time Segment 12:00 am - _____ _____ - _____ _____ - _____ _____ - _____	_____ U/hr _____ U/hr _____ U/hr _____ U/hr	
Temporary Basal Rate		 On  Off	
Bolus			
Target BG & Correct Above	Time Segment 12:00 am - _____ _____ - _____ _____ - _____ _____ - _____	Target _____ mg/dL _____ mg/dL _____ mg/dL _____ mg/dL	Correct Above _____ mg/dL _____ mg/dL _____ mg/dL _____ mg/dL
Insulin to Carb (IC) Ratio	Time Segment 12:00 am - _____ _____ - _____ _____ - _____ _____ - _____	1 unit of insulin covers _____ g _____ g _____ g _____ g	
Correction Factor	Time Segment 12:00 am - _____ _____ - _____ _____ - _____ _____ - _____	1 unit of insulin decreases BG by _____ mg/dL _____ mg/dL _____ mg/dL _____ mg/dL	
Duration of Insulin Action		_____ hours	
Maximum Bolus		_____ units	
Extended Bolus		 On  Off	

Physician Name \_\_\_\_\_ Signature \_\_\_\_\_ Date \_\_\_\_\_

Reference: Grunberger, G, Abelseth, J, Bode, B, et al. Consensus Statement by the American Association of Clinical Endocrinologist/American College of Endocrinology Insulin Pump Management Task Force. *Endocrine Practice*. 2014; 20 (5), 463-489.

1 PURPOSE

The purpose of this Statistical Analysis Plan (SAP) is to describe the statistical methodology that will be used to confirm the safety and effectiveness of the Omnipod Horizon™ Automated Glucose Control System in patients with type 1 diabetes. Should there be any discrepancy between the pivotal study protocol and this SAP, the content of the SAP shall prevail.

2 STUDY DESIGN

2.1 STUDY DESIGN OVERVIEW

This is a single-arm, multi-center, prospective clinical study. The study will be conducted in 12-20 clinical study sites in the United States. The study is expected to enroll up to 240 subjects in order to obtain 200 evaluable subjects with 100 subjects in each of two age cohorts (6-13.9 years and 14-70 years of age). Subjects will be considered evaluable if they have at least 8 weeks of data during Phase 2 of hybrid closed-loop.

2.2 INVESTIGATIONAL DEVICE

The Omnipod Horizon™ Automated Glucose Control System (“Horizon™ System”) is comprised of three primary components:

- Omnipod Horizon™ tubeless, insulin delivery alternate controller enabled (ACE) pump (Pod) with the Horizon™ algorithm
- Omnipod Horizon™ Personal Diabetes Manager (PDM) which is a Samsung J3 locked down Android device that operates the Omnipod Horizon™ App
- Dexcom G6 - Continuous Glucose Monitoring (CGM) system

In addition, the following non-investigational, commercially available devices will be used during the study:

- Contour® Next One blood glucose meter (Ascensia Diabetes Care, [name])
- Precision Xtra ketone meter (Abbott Diabetes Care Inc., [name])

2.3 STUDY SCHEDULE

The study will consist of a 14-day outpatient standard therapy (ST) outpatient phase (Phase 1), a 13-week outpatient hybrid closed-loop (HCL) phase (Phase 2), and a 6-month hybrid closed-loop extension phase (Phase 3). The sponsor intends to submit results from Phase 2 for marketing clearance after data collection for Phase 2 is complete.

A subset of subjects will participate in supervised challenges during any consecutive 5-day period during the 13-week HCL Phase 2:

- A minimum of 100 subjects 6-13.9 years

Statistical Analysis Plan

- A minimum of 60 subjects 14-70 years

Subjects having completed the prepivotal study may participate in this pivotal study and begin at Visit 5 during Phase 2 (HCL phase) since Phase 1 (ST) was completed as part of the prepivotal study and is not required to be repeated. Prepivotal subjects do not require rescreening if their original screening is within 45-days prior to Visit 5.

The Horizon™ System has two modes. In Manual Mode, the system will function equivalently to the Omnipod DASH System. This includes delivering insulin at programmed basal rates and bolus amounts with the option to set temporary basal profiles. In Automated Mode, the system will support the use of multiple target glucose values. The programmed basal rates, glucose targets and bolus calculator settings will inform the MPC (model predictive control) algorithm for insulin dosing parameters.

2.4 PHASE 2 HYBRID CLOSED-LOOP CHALLENGES

A subset of subjects will participate in supervised challenges during any consecutive 5-day period during the 13-week HCL Phase 2. All challenge days include both meal and exercise challenges as follows:

- Exercise (1-hour minimum of moderate intensity exercise and 2-hour minimum of mild intensity exercise)
- High carbohydrate meal ($\geq 60\text{g}$)

The meal challenges are divided up as follows:

- Day 1: Matched Meal Days 1 and 2, with bolus
- Day 2: Matched Meal Days 1 and 2, no bolus
- Day 3: Matched Meal Days 3 and 4, with bolus
- Day 4: Matched Meal Days 3 and 4, no bolus
- Day 5: Meal with bolus

Every effort will be made to conduct challenges over 5 consecutive days however challenges that occur on non-consecutive days will not constitute a protocol deviation. Challenge visits may occur on the same date as any other Phase 2 visit.

2.5 STUDY SUCCESS

The study will be deemed successful if the incidence rates of severe hypoglycemia and diabetic ketoacidosis during Phase 2 are considered acceptable compared to published rates.

2.6 RANDOMIZATION

This is a single-arm, multicenter, prospective clinical study where all eligible subjects will use the investigation device. Subjects will not be randomized.

2.7 POINT OF ENROLLMENT

A subject is enrolled in the study upon placement of the first study CGM. Subjects who do not meet the eligibility criteria will not continue in the study and will be considered screen failures.

Statistical Analysis Plan

2.8 DEFINITION OF PHASE 2 AND PHASE 2 PARTICIPATION

For the majority of subjects, Phase 2 of hybrid closed-loop data will include both data collected prior to a study pause and data collected after the recommencement. Unless otherwise specified, any data that may have been collected during a study pause (including but not limited to CGM readings from the Horizon system while in Manual Mode), will be excluded from analyses.

Continuous Phase 2 participation refers to the length of time on the Horizon system (either in Automated or Manual Modes) and is calculated as:

- Commencement of Phase 2 until a study pause (for subjects who started Phase 2 prior to a study pause)
- Recommencement until discontinuation from the Horizon system or end of Phase 2 (for subjects who started Phase 2 prior to a study pause)
- Commencement of Phase 2 until discontinuation from the Horizon system or end of Phase 2 (for subjects who started Phase 2 after a study pause)

If a subject has ≥ 6 weeks on the Horizon system during Phase 2 prior to a study pause and ≥ 6 weeks on the Horizon system during Phase 2 after the recommencement, the longer interval will be used for analysis of A1C. Specifically, the A1C associated with the longer interval, if available, will be used for the analysis of the A1C endpoints.

3 STUDY OBJECTIVES AND ENDPOINTS

3.1 SAFETY OBJECTIVE AND ENDPOINTS

The safety objective is to evaluate the safety of the Omnipod Horizon™ Automated Glucose Control System in patients with type 1 diabetes. The safety objective will be evaluated by summarizing the following events during Phase 2:

- Incidence rate of severe hypoglycemia (events per person months)
- Incidence rate of diabetic ketoacidosis (DKA) (events per person months)

3.2 PRIMARY EFFECTIVENESS OBJECTIVE AND ENDPOINTS

The primary effectiveness objective is to evaluate the effectiveness of the Omnipod Horizon™ Automated Glucose Control System. The primary effectiveness objective will be evaluated by analyzing the following endpoints:

- A1C after at least 6 weeks of continuous Phase 2 participation compared to baseline
- Percentage of time in range 70-180 mg/dL during Phase 2 of the HCL phase compared to Phase 1 (ST)

Statistical Analysis Plan

3.3 SECONDARY OBJECTIVE AND ENDPOINTS

The secondary objective is to evaluate additional glycemic measures of effectiveness of the Omnipod Horizon™ Automated Glucose Control System. The secondary objective will be evaluated based on the following per subject endpoints *with* prespecified hypotheses:

- Glucose metrics from system CGM during the hybrid closed-loop phase for Phase 2 will be compared to Phase 1 overall:
 - Percentage of time in range > 180 mg/dL
 - Percentage of time in range < 70 mg/dL

Additional per subject endpoints *without* prespecified hypotheses used to evaluate the secondary objective include:

- A1C:
 - A1C after at least 8 weeks of continuous Phase 2 participation at the end of Phase 2 (Visit 13), 6 months (Visit 16) and the end of Phase 3 (Visit 19)
 - Change from baseline in A1C after at least 6 weeks of continuous Phase 2 participation, after at least 8 weeks of continuous Phase 2 participation, at the end of Phase 2 (Visit 13), 6 months (Visit 16) and the end of Phase 3 (Visit 19)
 - Proportion of subjects demonstrating an improvement from baseline in A1C after at least 6 weeks of continuous Phase 2 participation, after at least 8 weeks of continuous Phase 2 participation, at the end of Phase 2 (Visit 13), 6 months (Visit 16) and the end of Phase 3 (Visit 19)
- Glucose metrics from system CGM during the hybrid closed-loop phase for Phase 2 and Phase 3 will be compared to Phase 1 during the day, overnight, and overall:
 - Mean glucose
 - Percentage of time in range 70-180 mg/dL
 - Percentage of time in range 70-140 mg/dL
 - Percentage of time in range > 180 mg/dL
 - Percentage of time in range ≥ 250 mg/dL
 - Percentage of time in range ≥ 300 mg/dL
 - Percentage of time in range < 70 mg/dL
 - Percentage of time in range < 54 mg/dL
 - Standard deviation
 - Coefficient of variation
- Percentage of time in hybrid closed-loop as proportion of overall device usage time during Phase 2 and Phase 3
- Glucose management indicator (GMI) based on overall mean glucose during Phase 2 and Phase 3 will be compared to Phase 1
- Insulin requirements during Phase 2 and Phase 3 will be compared to Phase 1:

Statistical Analysis Plan

- Total daily insulin (TDI) (units, units/kg)
- Total daily basal insulin (units, units/kg)
- Total daily bolus insulin (units, units/kg)
- Change from baseline in BMI (kg/m^2) at end of Phase 2 and Phase 3

4 ANALYSIS OF PRIMARY EFFECTIVENESS ENDPOINTS

There are two primary effectiveness endpoints. The primary effectiveness objective will be evaluated using the following endpoints:

- A1C after at least 6 weeks of continuous Phase 2 participation compared to baseline
- Percentage of time in range 70-180 mg/dL during Phase 2 of hybrid closed-loop phase compared to Phase 1 (standard therapy)

4.1 SAMPLE SIZE

This is a single-arm, multi-center, prospective study. The sample size and study duration were determined to allow for an adequate safety profile of the investigational device. The study will be claimed successful if the incidence rates of severe hypoglycemia and diabetic ketoacidosis are considered acceptable compared to published rates.

In addition, a statistically powered sample size was determined for the two primary effectiveness endpoints. Since each of the primary effectiveness endpoints will be evaluated separately, the significance level will be adjusted so that the overall type I error can be maintained at one-sided 2.5%, and each endpoint will be tested at one-sided 1.25%.

A1C

The sample size estimation is based on the following assumptions:

- Mean difference between paired observations of A1C after at least 6 weeks of continuous Phase 2 participation compared to baseline is -0.5%
- Standard deviation of the difference between paired observations of A1C after at least 6 weeks of continuous Phase 2 participation compared to baseline is 0.8%
- Power of 90% and one-sided significance level of 1.25%

The estimates for the mean difference and standard deviation of the difference between the paired observations were obtained from previous Omnipod studies, where subjects experienced a mean change in A1C of 0.38% over 3 months (standard pump therapy only), from 8.1 to 7.7%, n=85 (data on file). Based on the above assumptions, 35 subjects are required to provide evaluable data.

Statistical Analysis Plan

Percentage of Time in Range 70-180 mg/dL

The sample size estimation is based on the following assumptions:

- Mean difference between paired observations of percentage of time in range 70-180 mg/dL during Phase 2 of hybrid closed-loop compared to the Phase 1 is 10%
- Standard deviation of the difference between paired observations of percentage of time in range 70-180 mg/dL during Phase 2 of hybrid closed-loop compared to Phase 1 is 15%
- Power of 90% and one-sided significance level of 1.25%

The estimates for the mean difference and standard deviation of the difference between the paired observations were obtained from recent Omnipod Horizon feasibility studies, G170012 and G170143, where subjects experienced a mean change in percentage of time in range 70-180 mg/dL of $10.0 \pm 15.1\%$ and $13.8 \pm 14.6\%$, respectively. Based on the above assumptions, 31 subjects are required to provide evaluable data.

To gather adequate safety and effectiveness data on the performance of the Omnipod Horizon™ System, the study plans to enroll up to 240 subjects to obtain a minimum of 200 evaluable subjects equally distributed across two age cohorts (6-13.9 years and 14-70 years). Subjects will be enrolled at up to 20 clinical study sites. No single site should enroll more than 24 subjects for each age cohort.

A subset of subjects will take part in the prescribed exercise challenges per the defined sample sizes until the minimum number of subjects for each cohort subset has been satisfied.

4.2 PRIMARY ANALYSIS

There are two primary effectiveness endpoints. The primary effectiveness endpoints will not be used to support labeling claims.

A1C

A1C after at least 6 weeks of continuous Phase 2 participation will be compared to baseline A1C as measured by the core laboratory by calculating the change from baseline in A1C at the appropriate follow-up visit for each subject. Given the nature of this measure, continuous device use is essential for unbiased measurement of A1C. Therefore, the follow-up A1C used in the analysis of this endpoint will include only data from the subjects with at least 6 weeks of continuous Phase 2 participation, either prior to study pause or after recommencement, depending on the length of continuous participation and availability of the A1C measurements. The A1C collected at the latest follow-up visit during Phase 2 will be used, assuming it was collected after at least 6 weeks of subject's participation in Phase 2.

Statistical Analysis Plan

The change in A1C is calculated as the A1C at follow-up minus baseline A1C. The null hypothesis associated with this endpoint states that the mean change in A1C is greater than or equal to zero. Rejection of the null hypothesis indicates that the observed data support the alternative hypothesis that the mean change in A1C is less than zero (indicating improved glycemic control). The hypotheses associated with the first primary effectiveness endpoint are defined as:

$$\begin{aligned} H_0: \mu &\geq 0 \\ H_1: \mu &< 0 \end{aligned}$$

where μ is the mean of the per subject differences in A1C from baseline to follow-up.

Percentage of Time in Range 70-180 mg/dL

The percentage of time in range (TIR) 70-180 mg/dL during Phase 2 of hybrid closed-loop will be compared to standard therapy by calculating the change between the time in range percentages between Phase 2 of HCL and Phase 1 (ST) for each subject. The change is calculated as the percentage of time in range during Phase 2 minus the percentages of time in range during Phase 1. The null hypothesis associated with this endpoint states that the mean change in percentage of time in range 70-180 mg/dL is less than or equal to zero. Rejection of the null hypothesis indicates that the observed data support the alternative hypothesis that the mean change in percentage of time in range 70-180 mg/dL is greater than zero. The hypotheses associated with the second primary effectiveness endpoint are defined as:

$$\begin{aligned} H_0: \mu &\leq 0 \\ H_1: \mu &> 0 \end{aligned}$$

where μ is the mean of the per subject differences in percentage of time in range 70-180 mg/dL during Phase 2 hybrid closed-loop compared to the standard therapy phase (Phase 1).

Both primary effectiveness endpoints will be tested independently of each other for statistical significance using a paired t-test at a one-sided significance level of 1.25%.

The modified Intention to Treat (mITT) analysis set will be the primary analysis set used to analyze the primary effectiveness endpoints. The results based on the Per Protocol (PP) analysis set will be considered supportive.

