## 9.10 Unscheduled Visits (Phase 2)

Aside from scheduled visits, subjects may require an unscheduled visit either by telephone (inclusive of email or text options) or in person at the clinical study site. All scheduled assessments will be performed according to Table 2: Schedule of Assessments for Phase 1 and Phase 2. This visit will include, at a minimum:

- Review of concomitant medications
- Assessment of AEs since last visit
- Complaints/device deficiencies such as occlusion alarms and system hazard alarms since last visit
- Device uploads for BG and ketone meter (recommendation only if visit is conducted at the clinical site)
- Data review of Automated Mode use by clinician

During the Phase 2 study pause, subjects that wish to continue to use the Omnipod Horizon™ System in Manual Mode or subjects that wish to go back to using their own system during the pause will have either telephone or in person visits every 4 weeks  $\pm$  5 days from their last scheduled or unscheduled visit until the study resumes.

Subjects will continue to be provided study supplies during the study pause if they wish to continue in the study.

If subjects have been in the pivotal hybrid closed-loop phase for  $\geq$  35 days prior to pausing Automated Mode, subjects may be requested to submit to an A1C lab draw as soon as possible after pausing Automated Mode. The A1C lab draw does not have to coincide with a scheduled or an unscheduled visit.

Sites will ensure subjects that are continuing to use the system in Manual Mode do not enter Automated Mode during the study pause.

- Sites will be asked to check the Horizon Data portal once per week to make sure subjects have not entered Automated Mode
- If a subject is found to be in Automated Mode, the subject will be given a warning. If the same subject is found to be in Automated Mode a second

time, the subject will be instructed to return the investigational device to the site until a software fix is available

Subjects that do not wish to continue their study participation will be withdrawn from the study.

Additional assessments may be warranted at the discretion of the investigator.

Instructions will be given to subjects on how to contact clinical study staff 24 hours per day to report any study related problems. Subjects will be encouraged to call the clinical study site at any time with any concerns.

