#### 13.2.2.1 Primary Effectiveness Endpoints

There are two primary effectiveness endpoints.

- A1C after at least 6 weeks of continuous Phase 2 participation compared to baseline
- A1C at Visit 16, 19, 21, and 23 compared to baseline
- Percentage of time in range (70-180 mg/dL) during Phase 2 and separately during Phase 3 of the hybrid closed-loop phase as compared to Phase 1 (standard therapy)

#### A1C – Phase 2

A1C after at least 6 weeks of continuous Phase 2 participation will be compared to baseline A1C as measured by the core laboratory by calculating the change from baseline in A1C at the appropriate follow-up visit for each subject. Given the nature of this measure, continuous device use is essential for unbiased measurement of A1C. Therefore, the follow-up A1C used in the analysis of this endpoint will include only data from the subjects with at least 6 weeks of continuous Phase 2 participation, either prior to study pause or after recommencement, depending on the length of continuous participation and availability of the A1C measurements. The A1C collected at the latest follow-up visit during Phase 2 will be used, assuming it was collected after at least 6 weeks of subject's participation in Phase 2.

The change in A1C is calculated as A1C at follow-up minus baseline A1C (where negative change indicates decrease or improvement in A1C). The null hypothesis associated with this endpoint states that the mean change in A1C is greater than or equal to zero. Rejection of the null hypothesis indicates that the observed data support the alternative hypothesis that the mean change in A1C is less than zero.

The hypotheses associated with the first primary endpoint are defined as:

$$H_0: \mu \geq 0$$

$$H_1: \mu < 0$$

where  $\mu$  is the mean of the per subject differences in A1C from baseline to follow-up.

#### A1C – Phase 3

A1C at Visit 16 (~6 months total HCL participation) will be compared to baseline A1C as measured by the core laboratory by calculating the change from baseline in A1C at follow-up visit for each subject.

The change in A1C is calculated as A1C at follow-up minus baseline A1C. There are no hypotheses associated with this endpoint.

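### The sentence that picks the latest Phase 2 A1C drops the continuity condition and conflicts with the longer-interval rule and the endpoint's own definition

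*SAP*

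**What the plan says.** Four pieces of text decide which A1C enters the first primary endpoint.

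- **Eligibility (SAP 4.2; same text in protocol 13.2.2.1).** The follow-up A1C "will include only data from the subjects with at least 6 weeks of continuous Phase 2 participation", before the pause or after recommencement, "depending on the length of continuous participation and availability of the A1C measurements". The paragraph gives its reason: without continuous device use the A1C measurement would be biased.
- **Longer interval (SAP 2.8; same text in protocol 13.1).** When the segments before and after the pause are both at least 6 weeks, "the A1C associated with the longer interval, if available, will be used for the analysis of the A1C endpoints".
- **Latest visit (last sentence of the same SAP 4.2 paragraph; same text in protocol 13.2.2.1).** "The A1C collected at the latest follow-up visit during Phase 2 will be used, assuming it was collected after at least 6 weeks" of the subject's participation in Phase 2. The word *continuous* is absent.
- **Where a pre-pause A1C comes from (protocol 9.10).** For those with at least 35 days before the pause, "subjects may be requested to submit to an A1C lab draw as soon as possible after pausing Automated Mode". The draw is discretionary and need not fall on a study visit.

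SAP 2.8 defines the continuous form only: "Continuous Phase 2 participation refers to the length of time on the Horizon system", counted separately for each segment. Plain participation is not defined. The worked example in protocol 9.11 counts it cumulatively: after 28 days before the pause, the first day back is Day 29.

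**The concern.** The latest-visit sentence neither limits the choice to the longer interval nor asks for 6 continuous weeks before the draw. Read as written, it selects Visit 13 for every completer, which leaves the longer-interval rule with no work to do for them. For some completers it also selects a value that the rest of the paragraph treats as unsuitable.

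The clause giving the SAP precedence over the protocol (SAP 1, protocol 13.11) does not help, because both rules stand in the SAP. The pause is not a rare event either: SAP 2.8 expects most subjects to have Phase 2 data from both sides of it.

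At stake is the reported mean change in A1C in an open, single-arm study. Two analysts could follow the same plan and report different means. Where a subject has both draws, the choice could be made with both values in view.

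**Working it through.** **The plan's own figure first.** SAP 4.1 requires 35 subjects for a mean change of -0.5, SD 0.8, 90% power and one-sided 1.25%. The standardised effect is 0.5/0.8 = 0.625. A paired t-test with the noncentral t distribution gives n = 35 (power 0.906); the normal approximation gives 32. The figure reproduces and does not depend on this point.

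**Inputs for the day count.**
- P = days on the system in Phase 2 before the pause.
- T = total Phase 2 days at the last A1C. Visit 13 is Day 94, window 91 to 97 (protocol Table 2).
- Segment after the pause = T - P. This follows protocol 9.11, whose example is consistent: if 1 May is Day 29, Day 38 is 10 May, as stated there.
- 6 weeks = 42 days.

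**The two readings.**
- *Continuous reading* (SAP 2.8 plus the eligibility sentence): keep segments of at least 42 days; if both qualify, take the A1C of the longer.
- *Latest-visit reading*: take the last A1C if T is at least 42.

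**Thresholds at T = 94.**
- Both segments qualify when P ≥ 42 and 94 - P ≥ 42, so P = 42 to 52.
- The pre-pause segment is longer when P > 94 - P, so P ≥ 48 (48 against 46 days).
- The post-pause segment falls below 42 days when 94 - P ≤ 41, so P ≥ 53.
- At P = 47 the segments tie at 47 days. SAP 2.8 is silent on ties; I count this as agreement on Visit 13.

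**Subject completes to Day 94 and a pre-pause A1C exists:**

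| Pre-pause days | Post-pause days | Continuous reading | Latest-visit reading |
|---|---|---|---|
| up to 47 | 47 or more | Visit 13 | Visit 13 |
| 48 to 52 | 46 to 42 | pre-pause draw | Visit 13 |
| 53 or more | 41 or fewer | pre-pause draw | Visit 13 |

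In the last row SAP 2.8 no longer applies, because only one segment qualifies. There the conflict is with the 6-continuous-weeks requirement itself. With P = 60, for example, Visit 13 comes after 94 - 60 = 34 continuous days.

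**Subject completes to Day 94 and no pre-pause A1C was drawn:**

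| Pre-pause days | Continuous reading | Latest-visit reading |
|---|---|---|
| up to 47 | Visit 13 | Visit 13 |
| 48 to 52 | chosen value unavailable, fallback not stated; Visit 13 is the only candidate | Visit 13 |
| 53 or more | no eligible value | Visit 13 |

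**Across the Visit 13 window.** At T = 91 the pre-pause segment is the longer of two qualifying segments for P = 46 to 49, and the post-pause segment fails from P = 50. At T = 97 the figures are 49 to 55 and 56. The crossover therefore lies between 46 and 49 days.

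**Early withdrawal after recommencing.** The readings can part below 48 days. With T = 70 and P = 42 the post-pause segment is 28 days, so the continuous reading takes the pre-pause draw (if made) and the latest-visit reading takes the withdrawal A1C.

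**The case against.** The strongest reply is that the last sentence should be read inside its paragraph, as the latest value within the chosen interval. Three things support that. The endpoint is defined everywhere by continuous participation (SAP 3.2, 4, 4.2). The preceding sentence already makes the choice depend on segment length and A1C availability. And SAP 7.6 separately lists, as exploratory, the A1C change at the last follow-up visit after 6 weeks of Phase 2 participation; a primary endpoint read the same way would largely duplicate it.

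This makes the continuous reading the likelier intention, but the words for it are not in the text. The exploratory item also cuts the other way: it shows that the plan distinguishes plain from continuous participation, and the latest-visit sentence uses the plain form.

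A reader might be tempted to go further in four ways that the documents do not support.

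- *Every subject with about 48 or more pre-pause days is affected.* Not so. SAP 2.8 applies only if the A1C is available, and the pre-pause draw is discretionary. Someone who never recommences may have only one candidate value. The threshold also assumes completion to Visit 13.
- *A subject with 30 days before and 30 after the pause is let in.* The eligibility sentence already excludes that subject; the last sentence only picks a value for subjects who are included.
- *The shift in the mean can be estimated.* It is the share of subjects affected times the difference between the two draws. The documents give neither.
- *The primary conclusion is in danger.* With the planning SD of 0.8 and 200 subjects the standard error is 0.8/√200 = 0.057, so the assumed 0.5 is about 8.8 standard errors from zero. Study success rests on severe hypoglycemia and DKA rates (SAP 2.5), and SAP 4.2 says the primary effectiveness endpoints will not support labeling claims.

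**Conclusion.** The point holds for a defined group, and the last sentence is wrong as written. For completers to Day 94 with a pre-pause A1C, the plan gives two answers at 48 to 52 pre-pause days (crossover 46 to 49 over the visit window). From 53 days it points to a value that fails the endpoint's own definition. Without a pre-pause draw, Visit 13 is the only candidate at 48 to 52 days; from 53 days the choice is between a missing value and Visit 13.

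This rests on counting participation cumulatively across the pause, as protocol 9.11 does, and on taking the latest-visit sentence literally. How many subjects fall in the affected ranges, and how far the mean would move, cannot be computed from the documents. The sample size is unaffected and the test against zero is unlikely to change. The reported mean change could differ. This is a correction to make before the analysis, not a threat to the trial's main conclusion.

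**What to change.** Replace the last sentence of the A1C paragraph in SAP 4.2 and protocol 13.2.2.1 with one ordered rule:

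1. Identify each interval of at least 42 continuous days of Phase 2 participation.
2. If there are two, use the A1C tied to the longer one, counting a draw made just after pausing as tied to the pre-pause interval.
3. If that A1C is not available, use the A1C tied to the other qualifying interval.
4. Otherwise the subject has no primary A1C.

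The same text can settle the 47/47-day tie in either direction. Report the latest-available A1C as a sensitivity analysis. It is close to the exploratory endpoint already listed in SAP 7.6, but that list is only to be considered, so the analysis should be committed to.

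The cost is a wording change in two documents and one table, settled before the Phase 2 analysis. No extra visits, blood draws or subjects are needed.
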